6.2 Phase I Portion

To determine the MTD of the combination of thalidomide, lenalidomide and dexamethasone (LTD), with 4 dose levels planned. Dosing will start at doses of LTD that are intermediate intensity because of overlapping side effect profile of lenalidomide and thalidomide to determine the MTD and maximize the overall response rate of the regimen.

Table 6-1 Dose Levels to be studied

Dose Level	Assigned Therapy
Level -1	15 mg Lenalidomide daily on days 1-21 followed by 7-day rest every 28 days 50 mg Thalidomide daily 40 mg dexamethasone *
Level 1	15 mg Lenalidomide daily on days 1-21 followed by 7-day rest every 28 days 100 mg Thalidomide daily 40 mg dexamethasone *
Level 2	25 mg Lenalidomide daily on days 1-21 followed by 7-day rest every 28 days 100 mg Thalidomide daily 40 mg dexamethasone *
Level 3	25 mg Lenalidomide daily on days 1-21 followed by 7-day rest every 28 days 200 mg Thalidomide daily 40 mg dexamethasone

* Dexamethasone dosing for cycle 1-2: 40 mg days 1-4, 9-12, and 17-20; all subsequent cycles: 40 mg days 1,8, 15, 21

Dose Escalation

The first cohort of three patients enrolled into the study will receive dose level 1. A full safety evaluation will be conducted when these subjects have completed one cycle (28 days) of combination therapy.

Definition of DLT

A DLT will be defined as follows:

- Hematologic dose-limiting toxicity will be defined as either Grade 4 neutropenia lasting for ≥ 7 days in duration, any Grade 4 thrombocytopenia, or any Grade 5 hematologic toxicity. At least three patients in each cohort must be evaluable for hematologic toxicity.
- Non-hematologic dose-limiting toxicity will be defined as any Grade 3, 4 or 5 non-hematologic toxicity, with the specific exception of:
 - Isolated Grade 3 elevation of liver function tests (LFTs) without associated clinical symptoms, lasting for ≤ 7 days in duration.
 - Isolated Grade 3 elevation of amylase without associated clinical symptoms
 - Grade 3 hypocalcemia, hypokalemia, hypomagnesemia, hyponatremia, or hypophosphatemia which responds to medical intervention.

Definition of Maximum Tolerated Dose:

The MTD of the combination of lenalidomide, thalidomide and dexamethasone in multiple myeloma subjects shall be defined at the end of the trial, the dose with the smallest absolute value of (*posterior mean of pi-pT*) among all the tried doses *i* for which $T_i=0$ will be selected as the MTD.

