7.0 Statistical Consideration

This is an open label, phase I/II clinical trial to evaluate the safety and efficacy of lenalidomide, thalidomide, and dexamethasone in patients with relapsed/refractory multiple myeloma. The maximum number of patients that will be recruited for the study is 64.

Phase I design:

The objective of the phase I portion is to determine the maximum tolerated dose (MTD) of the combination regimen of lenalidomide, thalidomide, and dexamethasone. There are four predefined dose levels for lenalidomide, thalidomide, and dexamethasone, and the first cohort of patients will be treated at the second dose (Dose Level 1).

Dose Level	Assigned Therapy
Level -1	15 mg Lenalidomide daily on days 1-21 followed by 7-day rest every 28 days 50 mg Thalidomide daily 40 mg dexamethasone *
Level 1	15 mg Lenalidomide daily on days 1-21 followed by 7-day rest every 28 days 100 mg Thalidomide daily 40 mg dexamethasone *
Level 2	25 mg Lenalidomide daily on days 1-21 followed by 7-day rest every 28 days 100 mg Thalidomide daily 40 mg dexamethasone *
Level 3	25 mg Lenalidomide daily on days 1-21 followed by 7-day rest every 28 days 200 mg Thalidomide daily 40 mg dexamethasone

Dose limiting toxicity (DLT) is defined as in the treatment plan. To find the MTD, a statistical design based on a Bayesian model described in Ji, Li, and Bekele (2006) will be used. The details of the design are described below.

Let p_i denote the toxicity probabilities for dose $i=1, 2, 3, \text{ and } 4$. The goal is to accurately estimate the probability of toxicity at the current tried dose level. Assuming a vague independent beta prior $B(0.005, 0.005)$ for each p_i , with observed data (n_i, x_i) , where n_i represents the number of patients treated at current dose and x_i represents the number of patients experienced DLTs, the posterior of p_i follows an independent $B(0.005 + x_i, 0.005 + n_i - x_i)$ for $i=1, 2, 3, \text{ and } 4$. Let

$$T_i = 1\{P(p_i > p_T \mid \text{data}) > \xi\}$$

We define the posterior probabilities of three possible actions as

$$q(D, i) = P(p_i > p_T + K_1 \sigma_i \mid \text{data})$$

$$q(S, i) = P(p_T - K_2 \sigma_i \leq p_i \leq p_T + K_1 \sigma_i \mid \text{data})$$

$$q(E, i) = P(p_i < p_T - K_2 \sigma_i \mid \text{data}) * (1 - T_i)$$

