where D represents the action of de-escalating to next lower level, S represents staying at current dose and E represents escalating to next higher level, and σ_i is the posterior deviation of p_i . The dose-assignment rule B_i is defined as $B_i^{(e)} = \arg \max_{m \in \{D, S, E\}} q(m, i)$.

[figure not shown]
Based on dose-assignment rule $B_i^{(e)}$, a dose-finding algorithm is proposed as follows:

- 1) Suppose that Dose 1 is a dose that has been tried previously. If $T_i = 1$, terminate the trial due to excessive toxicity. Otherwise, terminate the trial when the maximum sample size is reached.
- 2) At current tried dose i , the decision to select the dose for next cohort are among $\{(i-1), i, (i+1)\}$ based on the assignment rule. There are two exceptions, however: if $i=1$, the next available doses are $\{1, 2\}$; if $i=4$, the next available doses are $\{3, 4\}$.
- 3) At the end of the trial, the dose with the smallest absolute value of (*posterior mean of $p_i - p_T$*) among all the tried doses i for which $T_i=0$ will be selected as the MTD.

Let $\xi = 0.95$, $K_1=1$ and $K_2=1.5$. Starting at Dose Level 1 (the second dose), the trial will enrol patients in a cohort size of three. The maximum sample size is 18 and the MTD has a probability of toxicity $p_T=0.4$. Table 1 presents the monitoring rules for each dose and Table 2 presents the operating characteristics of the proposed design under six toxicity scenarios. When MTD is among the doses studied (Scenarios 1, 2, and 3), this dose will be selected with the highest probability and the number of patients treated at this dose will be the largest among all doses. If all the Dose levels turn out to be too toxic (Scenario 6), the chances of these doses being selected are very low and most of the few patients treated will be at the lowest dose level. On the other hand, if all the Dose levels are below the MTD (Scenario 5), the highest dose will be chosen with the highest probability and most patients will be treated at the highest dose.

Table 1. Dose-finding trail-monitoring chart

		Number of patients treated at current dose																	
		1	2	3	4	5	6	7	8	9	10	11	12	13	14	15	16	17	18
Number of toxicities	0	E	E	E	E	E	E	E	E	E	E	E	E	E	E	E	E	E	E
	1	D U	S	S	S	E	E	E	E	E	E	E	E	E	E	E	E	E	E
	2		D U	S	S	S	S	S	S	E	E	E	E	E	E	E	E	E	E
	3			D U	D	S	S	S	S	S	S	S	S	E	E	E	E	E	E
	4				D U	D	D	S	S	S	S	S	S	S	S	S	E	E	E
	5					D U	D	D	D	D	S	S	S	S	S	S	S	S	S
	6						D U	D	D	D	D	D	S	S	S	S	S	S	S

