	7							D U	D	D	D	D	D	D	S	S	S	S	S
	8								D U	D	D	D	D	D	D	D	S	S	S
	9									D U	D	D	D	D	D	D	D	D	S
	10										D U	D	D	D	D	D	D	D	D
	11											D U	D	D	D	D	D	D	D
	12												D U	D	D	D	D	D	D
	13													D U	D	D	D	D	D
	14														D U	D	D	D	D
	15															D U	D	D	D
	16																D U	D	D
	17																	D U	D
	18																		D U

E = Escalate to next higher dose

S = Stay at current dose

D = De-escalate to next lower dose

U = Current dose is unacceptable

Table 2. Operating characteristics

Scenario		Dose -1	Dose 1	Dose 2	Dose 3	Total # of Pts	Overall Toxicity
1	Toxicity Rate	0.4	0.55	0.65	0.65	17.568	0.535121
	Chance Selected	0.507	0.313	0.08	0.015		
	# of Pts Treated	5.799	6.069	5.322	0.378		
2	Toxicity Rate	0.05	0.1	0.4	0.6	18	0.366222
	Chance Selected	0.002	0.17	0.703	0.125		
	# of Pts Treated	0.432	3.321	11.718	2.529		
3	Toxicity Rate	0.05	0.1	0.15	0.4	18	0.287222
	Chance Selected	0	0.003	0.232	0.765		
	# of Pts Treated	0.012	0.48	7.164	10.344		
4	Toxicity Rate	0.2	0.35	0.55	0.6	17.979	0.435675
	Chance Selected	0.12	0.53	0.322	0.025		
	# of Pts Treated	2.073	7.074	7.941	0.891		
5	Toxicity Rate	0.05	0.1	0.15	0.2	18	0.184056
	Chance Selected	0	0.005	0.114	0.881		
	# of Pts Treated	0.03	0.315	5.991	11.664		
6	Toxicity Rate	0.5	0.6	0.65	0.7	17.16	0.574242
	Chance Selected	0.492	0.233	0.078	0.004		
	# of Pts Treated	6.216	5.283	5.388	0.273		

Phase II design:

During the phase II portion of the study, patients will be treated with lenalidomide, thalidomide, and dexamethasone in combination at the MTD established in the phase I portion. Furthermore, the patients treated at the MTD in the phase I portion of the study will be considered the first patients of the phase II portion. It is anticipated that at least 6 patients will be treated at the MTD in the phase I and will be later included in the analysis of the phase II portion.

Response will be assessed after 4 cycles of therapy.

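### The Phase I decision chart (Table 1) does not follow from the stated rule: it prints Stay at 2 DLTs in 3 patients, where the rule de-escalates, and it omits the unacceptable flag in 20 cells at cohort sizes

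*Combined protocol and SAP*

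**What the plan says.** The Phase I design in section 7.0 leaves nothing to discretion. It sets out the model ("Assuming a vague independent beta prior", with both parameters 0.005), the target DLT probability p_T = 0.4, the constants K1 = 1, K2 = 1.5 and ξ = 0.95, and the three action probabilities q(D), q(S) and q(E). The action with the largest probability is taken. An indicator T_i equals 1 when the posterior probability that p_i exceeds 0.4 is above 0.95.

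The algorithm uses these as follows:

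- Step 1 stops the trial for toxicity on T at the lowest dose. It begins: "Suppose that Dose 1 is a dose that has been tried previously".
- Step 2 picks the next dose by the assignment rule and bars moves beyond either end of the dose range ("There are two exceptions, however").
- Step 3 selects the MTD only among tried doses with T = 0.

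The maximum is 18 patients, and "the trial will enrol patients in a cohort size of three". Section 6.2 adds: "The first cohort of three patients enrolled into the study will receive dose level 1".

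The text then states: "Table 1 presents the monitoring rules for each dose". In that chart the row for two toxicities reads D U at n = 2 and S from n = 3 to n = 8. The legend gives "U = Current dose is unacceptable", and U is printed only where the number of toxicities equals the number of patients.

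**The concern.** Table 1 is the form of the rule that the clinic will use, and it should be a mechanical consequence of the formulas. If a cell disagrees, the team holds two instructions for the same data.

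The 2/3 cell matters most, because it can occur in the first cohort at any dose. Above Level -1, the formula says go down one level and the chart says treat three more patients at a dose where two of three have just had a DLT. At Level -1 there is no conflict, since step 2 offers nothing lower.

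The U flags matter less but are not empty. T drives both termination at the lowest dose and eligibility for selection as MTD. A team that reads acceptability from the chart would miss most of the cells where the rule declares a dose unacceptable.

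**Working it through.** **Inputs (section 7.0).** Posterior Beta(0.005 + x, 0.005 + n − x); σ is its standard deviation; p_T = 0.4; K1 = 1; K2 = 1.5; ξ = 0.95.

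- q(D) = P(p > p_T + K1σ)
- q(S) = P(p_T − K2σ ≤ p ≤ p_T + K1σ)
- q(E) = P(p < p_T − K2σ) × (1 − T)
- T = 1 if P(p > 0.4) > 0.95

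**Reproducing the chart.** Computed for n = 1 to 18 and x = 0 to n (189 cells), the largest q agrees with the printed letter in 186 cells. That agreement shows the rule is being read as intended.

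**The 2/3 cell.** The posterior is Beta(2.005, 1.005), with σ = 0.2355. The limits are 0.4 + 0.2355 = 0.6355 and 0.4 − 1.5 × 0.2355 = 0.0467. This gives q(D) = 0.595, q(S) = 0.403 and q(E) = 0.002. The rule therefore gives D, and the chart prints S. P(p > 0.4) = 0.840, so T = 0.

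**The other two mismatches.** At 3/5, q(D) = 0.525 against q(S) = 0.472. At 4/7, 0.507 against 0.488. Both print S. Neither arises with full cohorts of three.

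**Could other constants explain it?** With everything else as stated, Stay at 2/3 needs K1 of about 1.35, which breaks six other cells. None of the variants of K1, K2, p_T and the prior that were tried reproduced every letter.

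**U flags.** T = 1 in 70 cells and the chart marks 18, so 52 are missing. Those at cohort sizes are:

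| n | x with T = 1 but no U | P(p > 0.4) at the smallest such x |
|---|---|---|
| 6 | 5 | 0.990 |
| 9 | 6–8 | 0.9502 (borderline) |
| 12 | 8–11 | 0.971 |
| 15 | 10–14 | 0.98 |
| 18 | 11–17 | 0.965 |

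That is 1 + 3 + 4 + 5 + 7 = 20 cells. All 52 print D, which is the correct action. No value of ξ yields the printed pattern: 1/1 is marked U at 0.9975, while 17/18 is unmarked at above 0.9999.

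**Consequences.** All paths were enumerated exactly, so there is no simulation error. The set-up was: start at Level 1, six cohorts of three, Table 2's true DLT rates, the written T rule kept in both versions, and ties in MTD selection going to the lower dose. A conflict is a 2/3 first cohort above Level -1 with another cohort still to come. As a hand check, the first cohort alone gives 3 × 0.55² × 0.45 = 0.408 in Scenario 1; first visits to higher levels bring this to 0.470.

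| Scenario | Trials with a conflict | Mean DLTs, rule | Mean DLTs, chart | Difference |
|---|---|---|---|---|
| 1 | 47% | 8.31 | 8.74 | 0.43 |
| 2 | 44% | 5.71 | 6.01 | 0.30 |
| 3 | 32% | 4.26 | 4.45 | 0.19 |
| 4 | 45% | 6.72 | 7.03 | 0.31 |
| 5 | 16% | 2.87 | 2.90 | 0.03 |
| 6 | 47% | 8.74 | 9.27 | 0.53 |

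The two scenarios where Level 1 is clearly too toxic, rule against chart:

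| | Scenario 1 (Level 1 rate 0.55) | Scenario 6 (Level 1 rate 0.60) |
|---|---|---|
| Mean patients at Level 1 | 8.2 vs 9.9 | 6.6 vs 8.5 |
| Level 1 chosen as MTD | 0.314 vs 0.366 | 0.181 vs 0.224 |
| Stopped for toxicity | 0.113 vs 0.099 | 0.280 vs 0.254 |

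If the chart's U replaced T, which the text does not instruct, stopping in Scenario 6 would fall to 0.104.

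**Table 2, a separate defect.** The first three patients are assigned to Level 1, so the mean count there cannot be below 3. Table 2 prints 0.48 (Scenario 3) and 0.315 (Scenario 5); the stated rule gives 4.5 in both. In Scenario 6 the mean total is 15.99 under the stated rule, against 17.16 printed.

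**The case against.** **The formula governs.** Step 2 selects the next dose by the assignment rule, and Table 1 only presents it. On that reading 2/3 is an error in a derived chart, not a true ambiguity. This is a fair reading, but there is no explicit order of precedence, and a clinical team is more likely to consult the chart than to integrate a beta density.

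**The missing U flags change little.** The legend never equates U with T = 1; that is an inference, though a natural one. All 52 cells already print D. When T = 1, P(p < 0.4) is below 0.05, so escalation could not win in any case. Termination and MTD eligibility are written out in steps 1 and 3 without reference to U. This stands: the flags are a secondary defect.

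**The chart is not uniformly worse.** Selection probabilities, rule against chart, are 0.690 vs 0.677 for Level 2 in Scenario 2, 0.660 vs 0.684 for Level 3 in Scenario 3, 0.654 vs 0.666 for Level 1 in Scenario 4, and 0.595 vs 0.608 for Level 3 in Scenario 5. This also stands. In Scenarios 2 to 5 selection is near neutral or slightly better under the chart. The clear cost falls in Scenarios 1 and 6, and the conflict percentages measure divergence, not harm.

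**Dose finding may be over.** Section 6.3 names the MTD regimen as lenalidomide 25 mg with thalidomide 100 mg, which is Level 2, and section 6.8.2 refers to a last Phase II cohort. Section 7.0 is still worded prospectively. If Phase I is complete, a new chart guides no further patient. The path to that MTD still matters, because Phase II patients are treated at it and Phase I patients treated at the MTD are counted in Phase II.

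**The chart was read from a PDF.** Lost U marks cannot be fully excluded. But U survives in all 18 diagonal cells and in no others, and the 2/3 finding does not depend on U.

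**Conclusion.** The point holds. Table 1 has one wrong action that full cohorts of three can reach, at 2/3, out of the 69 cells they can reach. It errs in the less cautious direction. It also lacks the unacceptable flag in 20 cohort-size cells (19 if the borderline 6/9 is set aside), where the printed action is nonetheless right.

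The effect is moderate: up to about half a DLT per trial, and 1.7 to 1.9 more patients at Level 1 when its true DLT rate is 0.55 to 0.60 (9.9 − 8.2 and 8.5 − 6.6). These sizes rest on full cohorts of three, the written T rule being applied in both versions, and Table 2's scenarios. If cohorts are incomplete or patients are added, the 3/5 and 4/7 errors can come into play as well.

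Table 2's counts at Level 1 are impossible under the stated start, so its operating characteristics are not those of the design described. That is a separate fault and does not follow from the chart. Both tables should be corrected.

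**What to change.** 1. Regenerate Table 1 by program from the stated prior, p_T, K1, K2 and ξ. It should print D at 2/3, 3/5 and 4/7, and U wherever T = 1. For cohorts of three, U starts at 3/3, 5/6, 6/9, 8/12, 10/15 and 11/18. State in the legend that U means T = 1.
2. Say in step 1 that termination uses T at the lowest dose, Level -1. The i = 1 to 4 indexing already implies this, but Table 2 labels Level 1 as Dose 1. Leave q(E,i) as printed.
3. Rerun Table 2 from the same program with the stated Level 1 start.
4. If dose finding is complete, check the Phase I decisions and report whether the rule or the chart was followed at any 2/3 cohort.

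The cost is one regenerated chart, one clarified sentence and one rerun simulation, plus a review of at most 18 / 3 = 6 cohort decisions if Phase I is over. No extra patients, visits or trial time are needed.

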The overall response and toxicity will be monitored simultaneously using the Bayesian approach of Thall, Simon, Estey (1995, 1996) as extended by Thall and Sung (1998). Historical data on similar patients show an overall response rate (ORR) of 30% and toxicity rate of 30%. However, the information was down-weighted to reflect the same marginal ORR and toxicity rates in 2 patients. Independence was assumed between OR and toxicity. It is expected for the current trial that the three-drug combination will improve the ORR to 50% while the toxicity rate is maintained at 40%. A sample size of 36 ensures that, if the trial is not terminated early, a posterior 90% credibility interval for overall response rate will have width of 0.26 at most, under the assumption of a 50% of ORR. The probabilities of OR and toxicity for the historical data are modeled by beta distributions ($Beta(3, 7)$ and $Beta(3, 7)$, respectively). The prior probabilities of OR and toxicity for the experimental regimen are also modeled by beta distributions ($Beta(0.6, 1.4)$ and $Beta(0.6, 1.4)$, respectively), which have the same a/b (a and b denote the parameters for a $Beta$ distribution) ratio as the beta distributions for the historical data. Denoting the historical probabilities of overall response rate and toxicity rate by $\{p(OR,H), p(TOX,H)\}$, the following decision criteria will be applied:

- 1) Let E correspond to the experimental treatment, stop if $\text{Prob}\{p(OR,H) + \delta_{OR} > p(OR,E) | \text{data}\} > 0.90$, where $\delta_{OR} = 0.20$
- 2) Stop if $\text{Prob}\{p(TOX,H) + \delta_{TOX} < p(TOX,E) | \text{data}\} > 0.85$, where $\delta_{TOX} = 0.10$

Patients will be monitored according to the following stopping boundaries for overall response.

Number of patients evaluated	Recommend stopping if \leq OR observed
12	3
24	7
36	11

At the same time, patients will be monitored according to the following stopping boundaries for toxicity.

Among these number of patients	Recommend stopping if \geq toxicity observed
12	8
24	15
36	22

The operating characteristics are summarized in the following table (based on simulations from 10,000 trials).

True Toxicity Rate	True OR Rate	Prob(stop the trial early)
0.1	0.3	0.654
	0.4	0.296
	0.5	0.086

	0.6	0.016
	0.7	0.002
0.25	0.3	0.655
	0.4	0.298
	0.5	0.089
	0.6	0.019
	0.7	0.005
0.4	0.3	0.677
	0.4	0.343
	0.5	0.147
	0.6	0.082
	0.7	0.068
0.55	0.3	0.795
	0.4	0.583
	0.5	0.225
	0.6	0.417
	0.7	0.409

Analysis Plan

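### The phase II early-stopping table assumes unselected patients, but the plan counts the phase I MTD patients first; at a true toxicity rate of 0.55 the early toxicity stop is then about 9-16%, not about 41%

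*Combined protocol and SAP*

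**What the plan says.** All of this is in section 7.0 of the combined protocol and SAP.

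- **MTD selection (phase I, step 3).** Among the tried doses not flagged as too toxic, the MTD is "the dose with the smallest absolute value of" the posterior mean toxicity probability minus the target, which is 0.40.
- **Phase I conduct.** "Starting at Dose Level 1 (the second dose), the trial will enrol patients in a cohort size of three", to a maximum of 18 patients.
- **Carry-over.** In phase II, "the patients treated at the MTD in the phase I portion of the study will be considered the first patients of the phase II portion". The plan adds: "It is anticipated that at least 6 patients will be treated at the MTD in the phase I", and these patients are later included in the phase II analysis.
- **Toxicity boundary.** Recommend stopping at 8 or more toxicities in 12 patients, 15 or more in 24, or 22 or more in 36. Carried-over patients are not exempted.
- **Support for the boundary.** "The operating characteristics are summarized in the following table (based on simulations from 10,000 trials"). The text does not say whether the simulation included the phase I selection step.

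Phase II toxicity is not defined. The only dose-limiting definition is the phase I DLT in section 6.2, where the safety evaluation follows one 28-day cycle.

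**The concern.** A dose becomes the MTD partly because the patients treated at it showed an acceptable DLT rate. If its true rate is well above 0.40, it is selected mainly in those trials where its observed rate happened to run low. Entering the same patients first in the phase II toxicity count gives the rule a favourable start exactly when the dose is too toxic. Often the look at 12 contains no new patient and only re-tests the data that chose the dose.

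The table of early-stopping probabilities is the plan's only quantitative support for the toxicity boundary. If it was computed for fresh patients, it overstates how often the planned trial would stop at an over-toxic dose.

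**Working it through.** **Step 1: reproduce the printed table.** Take all patients as independent at the true rate, with looks at 12 and 24.

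Toxicity component = P(X12 ≥ 8) + P(X12 ≤ 7 and X24 ≥ 15).
- At 0.40 this is 0.066.
- At 0.55 it is 0.408, of which 0.304 comes from the look at 12.

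At toxicity 0.10 the toxicity component is 0.000, so those printed cells are the response component alone: 0.654, 0.296, 0.086, 0.016 and 0.002 for ORR 0.3 to 0.7. The plan assumes that response and toxicity are independent, so early stop = 1 − (1 − toxicity)(1 − response). At toxicity 0.55:

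| ORR | Calculation | Result | Printed |
|---|---|---|---|
| 0.3 | 1 − 0.592 × 0.346 | 0.795 | 0.795 |
| 0.4 | 1 − 0.592 × 0.704 | 0.583 | 0.583 |
| 0.5 | 1 − 0.592 × 0.914 | 0.459 | 0.225 |
| 0.6 | 1 − 0.592 × 0.984 | 0.417 | 0.417 |
| 0.7 | 1 − 0.592 × 0.998 | 0.409 | 0.409 |

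Over the whole table, 19 of 20 cells agree to three decimals. The exception, 0.225, is out of order between 0.583 and 0.417 and looks like a misprint. Adding the look at 36 gives 0.463 in the last row, so the table counts only the looks at 12 and 24. It therefore describes unselected patients.

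**Step 2: simulate the plan as written.** Phase I uses the stated Beta(0.005, 0.005) prior, ξ = 0.95, K1 = 1, K2 = 1.5, target 0.40, cohorts of three, a start at Level 1 and at most 18 patients. The MTD is chosen by step 3. Its patients and DLTs become the first phase II patients, and new patients follow at the true rate. Phase II toxicity is taken to be the DLT (an assumption). Results are conditional on the dose being selected. Ranges cover decisions by printed Table 1 and by the formula, and at 0.40 and above 0.55 also the different scenarios.

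| True rate | Early toxicity stop with carry-over | Unselected patients |
|---|---|---|
| 0.40 | 0.01-0.03 | 0.066 |
| 0.55 (Scenario 1, Level 1) | 0.09-0.10 | 0.408 |
| 0.55 (Scenario 4, Level 2) | 0.16 | 0.408 |
| 0.60 | 0.15-0.34 | 0.587 |
| 0.65 (rarely selected) | 0.35-0.45 | 0.757 |

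At 0.55, counting the look at 36 gives about 0.16 (Scenario 1) and 0.24 (Scenario 4), against 0.46. With ORR 0.5, total early stopping is about 1 − 0.91 × 0.914 = 0.17 to 1 − 0.836 × 0.914 = 0.24, against 0.459.

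**Step 3: why it drops.** At 0.55 the carried-over patients average 11-15 and show an observed DLT rate of about 0.45-0.47. In roughly 52-85% of these trials at least 12 are already at the MTD. Selection explains the whole drop: unselected phase I patients would leave 0.408.

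A hand check with six carried over shows how the first look depends on their DLTs:
- With 2 DLTs, all six new patients must have toxicity: 0.55^6 = 0.028.
- With 3 DLTs, at least five of six must: 6 × 0.55^5 × 0.45 + 0.55^6 = 0.164.
- With 4 DLTs, the stop probability is 0.442.
- Twelve fresh patients give 0.304.

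Step 3 of the algorithm favours the lower counts.

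**Step 4: other readings.** Treating a dose as unacceptable only where Table 1 prints U gives 0.147 (Scenario 1) and 0.213 (Scenario 4). Starting at Level 2 gives about 0.14-0.18. Level 2 was tried because Table 2 does not fit the stated start: Scenarios 3 and 5 show 0.48 and 0.315 patients at Dose 1, where the first cohort alone needs three. Over all readings the range at 0.55 is 9-21%.

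**The case against.** **Using all data at the dose is a legitimate design choice.** The boundary is a posterior probability given the data, and pooling the phases is common. This stands, and it is why the remedy does not require dropping the carried-over patients. But the plan supports the boundary with simulated stopping frequencies, and those do not describe the plan as written.

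**The figures are conditional.** They hold at a true rate of 0.55 once that dose has been selected. Table 2 gives that a chance of 0.313 in Scenario 1 and 0.322 in Scenario 4. Simulating the stated start gives about 0.30-0.35 and 0.19-0.21. A reader might infer that any over-toxic dose is stopped only 9-16% of the time. The results at 0.60 and 0.65 do not support that.

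**Toxicity is undefined.** If events after cycle 1 also count, carried-over patients can add toxicities and the shortfall narrows. This stands as a condition.

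**Other safeguards exist.** A reader might infer that phase II is left without toxicity protection. The documents do not support that. They provide dose interruption and reduction (6.3.1, 6.3.2, 6.8.3, 6.11, Appendix B), discontinuation for adverse events (6.12), weekly investigator meetings (8.0) and the boundary at 36. The rule is reduced, not absent.

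**Few patients are affected.** At 0.55, applying the toxicity rule to new patients only would change the mean number of new phase II patients treated by about 1.5: roughly 20 against 18.5 in Scenario 1, and 22.4 against 21 in Scenario 4. That limits the practical harm. It does not make the table correct.

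**Conclusion.** The point holds. The phase II operating characteristics were computed for unselected patients, while the plan puts the selected phase I MTD patients first. At a true toxicity rate of 0.55, given selection of that dose, the early toxicity stop is about 9-16% under the stated design and at most about 21% under other readings, against about 41% behind the table.

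The size rests on phase II toxicity meaning the phase I DLT, on 36 including the carried-over patients when the look at 36 is counted, and on conditioning on selection. That the table omits selection does not depend on these: it follows from reproducing the printed cells. Tables 1 and 2 do not fully agree with the stated phase I rules, so the size is a range. No reading comes near 41%.

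**What to change.** **Needed.** Simulate phase I and phase II together with the carry-over as planned, and restate the early-stopping table on that basis. State two things in section 7.0:
- Whether the 36 patients include those carried over. The maximum of 64 equals 18 + 36 + 10 with no overlap, which does not fit counting the MTD patients within phase II.
- Whether phase II toxicity means the phase I DLT and, if not, which events and what period count.

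The cost is a rerun simulation and a few sentences.

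**Option for the sponsor to weigh.** Apply the toxicity boundary to newly enrolled phase II patients only, and keep the carried-over patients for ORR. Within 36 patients in total, at a true rate of 0.55:
- Early stops only: about 0.32-0.35, against 0.09-0.16 as planned.
- Looks up to the final patient included: about 0.33-0.39, against 0.16-0.24.

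At 0.40 the option gives about 0.06-0.07. It comes nearer to the printed 0.408 but does not restore it. It has three downsides: observed DLTs at the same dose no longer count, toxicity and response have different denominators although they are monitored together, and often only one toxicity look fits within 36. With 13 to 18 carried over, only 18 to 23 new patients remain.
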